# 12.1.3 The following will be monitored and documented daily as part of the standard of care

- Concomitant medications
- Adverse Events
- Interim Physical exam

- Vital signs (temperature, blood pressure, pulse rate, respiratory rate and oxygen saturation by pulse oximeter)
- Oxygen requirement (L/min)

# 12.1.4 The following will be monitored less frequently as part of standard of care and wherever possible

- For patients on concomitant hydroxychloroquine, a 12-lead electrocardiogram (if allowed by hospital treatment guidelines under COVID-19) approximately 3 hours after the first study drug administration on Day 1, anytime on Days 2 and 4, and again at end-of-treatment (either Day 14, 28 or at premature study drug discontinuation). If patients are on monitors (including telemetry or Holter monitors), investigators are encouraged to collect QT interval data
- Nasopharyngeal or oropharyngeal viral swab for SARS-CoV-2 PCR test every 1-3 days
- Serum chemistry once weekly
- Serum CRP, D-Dimer, LDH, ferritin, cardiac troponin once weekly
- CBC with differential once weekly
- Chest X-ray as per physician decision

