Screening/Basel ine Assessments	
 
Signed informed consent
 
Eligibility determination
 
Complete medical history (including onset of COVID-19 symptoms)
 
Concomitant medication assessment
 
Baseline review of systems
 
Physical examination
 
Vital signs (temperature, blood pressure, pulse rate, respiratory rate and oxygen saturation by pulse oximeter)
 
Weight if the patient is ambulatory
 
Oxygen requirement (L/min)
 
12-lead electrocardiogram
 
Chest Xray
 
Nasopharyngeal or oropharyngeal swab for SARS-CoV-2 PCR test
 
Serum chemistry
 
CRP, D-Dimer, LDH, ferritin, cardiac troponin
 
HbA1c
 
CBC with differential
 
	
	• Urinalysis	

	Serum pregnancy test (for women of childbearing potential) within 3 days prior to treatment	
Study Assessments	The following will be monitored and documented daily as part of the standard ocare:	
	Concomitant medications	
	Adverse Events	
	Interim Physical exam	
	Vital signs (temperature, blood pressure, pulse rate, respiratory rate and oxygen saturation by pulse oximeter)	
	Oxygen requirement (L/min)	
	The following will be monitored less frequently as part of standard of care and wherever possible:	
	• For patients on concomitant hydroxychloroquine, a 12-lead electrocardiogram (if allowed by hospital treatment guidelines under COVID-19) approximately 3 hours after the first study drug administration on Day 1, anytime on Days 2 and 4, and again at end-of-treatment (either Day 10, 14 or at premature study drug discontinuation). If patients are on monitors (including telemetry or Holter monitors), investigators are encouraged to collect QT interval data	
	Nasopharyngeal or oropharyngeal viral swab for SARS-CoV-2 PCR test every 1-3 days	
	Serum chemistry once weekly	
	Serum CRP, D-Dimer, LDH, ferritin, cardiac troponin once weekly	
	CBC with differential once weekly	
	Chest X-ray as per physician decision	
Study Endpoints	Primary	
	The total oxygen requirement (area under the curve) using the daily supplemental oxygen flow (L/min) over 14 days (Day 1 to Day 14)	
	Secondary	
	1) Time to 50% reduction from baseline in supplemental oxygen based on oxygen flow in L/min	

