#### 4 SCHEDULE OF ASSESSMENTS

Table 1 Schedule of Assessments for the Study

Assessments	Screening	Randomization	DB Phase		Early termination	Safety follow- up
	Days -3 - 1	Day 1	Day 7	Day 14	termination	ир
ICF signed	Х					
Inclusion/exclusio n criteria	х					
Demographics; medical and surgical history	x					
Review concomitant medication(s) 	х	х	Х	х	х	х
Review of adverse events 		х	X	х	x	x
Physical examination 	х		X	х	x	x
Vital signs 	Х	x	X	Х	Х	х
Oxygen flow (L/min) 	х	х	х	х	Х	х
Weight 	Х					
HbA1c	Х					
Pharyngeal viral sample 	х	х	х	х	х	х
12-lead ECG 	Х			Х		
Chest X-ray⁵	Х					
Serum chemistry	Х		Х	Х		
Hematology (CBC with differential)	Х		X	х		
D-dimer, cardiac troponin, CRP, LDH, ferritin 	x		X	х		
Urinalysis	Х					
Serum pregnancy test 	х					

<sup>1daily assessments whilst patient is hospitalized; vital signs = temperature, blood pressure, pulse rate, respiratory rate and oxygen saturation by pulse oximeter and recording of supplemental oxygen requirement as oxygen flow (L/min)

<sup>2 record weight if patient is ambulatory

<sup>3 pharyngeal samples for SARS-CoV-2 PCR are collected daily, per standard of care. For patients having nasopharyngeal swabs, the same nostril must be used during the study

<sup>4 for patients on concomitant hydroxychloroquine, the 12-lead ECG will be repeated after 3 hours (±30mins) of initial dose, on Day 2 and Day 4

<sup>5 Chest X-ray, lab draws will be at the discretion of the Investigator depending on patient clinical condition

<sup>6 CRP=C-reactive protein, LDH=lactate dehydrogenase

<sup>7 women of childbearing potential; serum pregnancy test must be negative within 3 days prior to randomization

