## **6.4.1 Completed Studies**

#### 6.4.1.1 Phase 1b Study in patients with advanced solid tumors (Study No. ABC-101)

Twenty-two patients were enrolled, of whom 21 were treated with doses from 250 mg QD through 750 mg BID. All 21 patients were evaluable for pharmacokinetics, pharmacodynamics and safety. Sixteen were evaluable for efficacy per RECIST 1.1 criteria. Patients received treatment continuously in 28

day cycles and treatment was given while fasting. Mean age of patients entered was 58 years. Seventy one percent were male, 67% white. All patients had received prior chemotherapy and approximately half had prior surgery and/or radiotherapy. Patients had a variety of concomitant medical conditions and were receiving a variety of medications in addition to their antitumor therapy.

The administered oral dose of 500 mg Q12 hours was the maximum tolerated dose. There were no deaths reported during the administration of opaganib. There were no discontinuations due to adverse events (AEs), in 250 mg QD and 250 mg bid cohorts. Common adverse events were nausea (12 patients, 57%), fatigue (12 patients, 57%), vomiting (8 patients, 38%) and neuropsychiatric effects (14 patients, 67%) including anxiety, insomnia, agitation and dysarthria. Of these, only fatigue appeared to be dose-related. Nausea and vomiting were common but not dose-limiting and rarely required discontinuation of treatment. Neuropsychiatric effects were seen at all dose levels, though were more common and bothersome at the highest dose level, 750 mg Q12 hours, considered an intolerable dose.

There were no consistent trends toward increases or grade shifts in liver function tests, hematologic parameters, or other biochemical parameters except for creatinine and lymphocytes. No patient developed clinically significant ECG abnormalities on study. There were no treatment group differences noted for the changes from baseline of QTcF. For more detailed data refer to Investigator Brochure.

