#### 9.2 Exclusion Criteria

- 1) Any co-morbidity that may add risk to the treatment in the judgement of the investigator.
- 2) Requiring intubation and mechanical ventilation
- 3) Patient having a do not intubate or do not resuscitate order
- 4) Oxygen saturation >95% on room air

- 5) Any preexisting respiratory condition that requires intermittent or continuous ambulatory oxygen prior to hospitalization
- 6) Patient is, in the investigator's clinical judgement, unlikely to survive >72 hours
- 7) Pregnant (positive serum test within 3 days prior to randomization) or nursing women
- 8) Unwillingness or inability to comply with procedures required in this protocol.
- 9) Corrected QT (QTc) interval on electrocardiogram (ECG) >470 ms for females or >450 ms for males, calculated using Friedericia's formula (QTcF)
- 10) AST (SGOT) or ALT (SGPT) > 5 x upper limit of normal (ULN)
- 11) Bilirubin >2x ULN (except where bilirubin increase is due to Gilbert's Syndrome)
- 12) Serum creatinine >2.0 X ULN
- 13) Absolute neutrophil count <1000 cells/mm^3
- 14) Platelet count <75,000/mm^3
- 15) Hemoglobin < 8.0 g/dL
- 16) Currently taking medications that are sensitive CYP3A4, CYP1A2, CYP2C9, CYP2C19 or CYP2D6 substrates and have a narrow therapeutic index. These should be decided in discussion with the Medical Monitor on a case-by-case basis.
- 17) Currently taking medications that are strong inducers or inhibitors of CYP2D6 and CYP3A4. These should be decided in discussion with the Medical Monitor on a case-by-case basis.
- 18) Currently taking warfarin, apixaban, argatroban or rivaroxaban
- 19) Current drug or alcohol abuse
- 20) Currently participating in a clinical study assessing pharmacological treatments, including antiviral studies

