#### 10 STUDY DESIGN

## **10.1 Overall Investigation Plan**

This is a phase 2a, proof of concept, multi-center randomized double-blind, parallel arm, placebo controlled study. The study is planned be performed in the US and in other countries, in approximately 15 clinical sites.

After informed consent is obtained, patients will enter a screening phase for no more than 3 days, to determine eligibility. Approximately 40 eligible patients will be randomized to receive either opaganib added to standard of care, or matching placebo added to standard of care, in a randomization ratio of 1:1. Treatment assignments will remain blinded to the patient, investigator and hospital staff, as well as the sponsor. As there is currently no consensus for a definitive treatment specifically targeting the SARS-CoV-2 virus causing COVID-19 (K. Wilson, 2020), standard of care will refer to regional, institutional or physician directed therapies, that may be implemented during the COVID-19 pandemic.

Study participants will receive either opaganib 2 x 250 mg capsules (500 mg) every 12 hours, or matching placebo, in addition to standard of care (pharmacological and/or supportive). Study drug will be administered every day for 14 days (Day 1 to Day 14), unless the patient has been discharged from the hospital without requiring supplemental oxygen, in which case study drug will only be administered to Day 10.

All participants will be followed up for 4 weeks after their last dose of study drug, which may occur at the end of the 2-week double-blind treatment phase or after premature study drug discontinuation, based upon patient or physician determination.

The maximum duration of study participation will be 45 days (including up to 3 days screening; 2 weeks double-blind (DB) phase and 4-weeks off-study drug follow-up).

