#### 10.3 Patient Discontinuation Criteria

A patient may be withdrawn from the study treatment or the study for any of the following reasons:

- Request of the patient or patient's representative
- The patient has experienced an AE that meets protocol defined stopping criteria (refer to Section 10.5.2)
- AEs or adverse device effects (ADEs) based on the judgment of the InvestigatorThe Investigator decides that it is in the patient's best interest
- The patient is noncompliant with the protocol

- Lost to follow-up
- Death

If a subject is withdrawn at any time, the reason(s) will be recorded in the relevant section of the eCRF. Patients who discontinue from study treatment and remain in the study, will continued to be monitored per the Schedule of Assessments until Day 14.

Patients discontinued due to AEs or ADEs will be monitored until resolution or stability of the event based on the judgment of the investigator.

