## 13.4 Safety

- 1) Incidence rates of all treatment-emergent AEs (TEAEs) and SAEs
- 2) Evaluation of vital signs
- 3) Evaluation of laboratory parameters (chemistry and hematology)
- 4) Evaluation of electrocardiograms (ECG)

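### Protocol 12.1.4 names the wrong end-of-treatment ECG days, and the SAP's Day 14 ECG summary mixes on-drug and off-drug recordings

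*Protocol*

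**What the plan says.** **Dosing.** Protocol 10.1 gives study drug from Day 1 to Day 14, except for a patient discharged without needing supplemental oxygen, "in which case study drug will only be administered to Day 10".

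**ECGs, patients on hydroxychloroquine.** Protocol 12.1.4 asks for ECGs about 3 hours after the first dose, on Days 2 and 4, and at end of treatment, which it explains as "either Day 14, 28 or at premature study drug discontinuation". The same bullet in the synopsis (Study Assessments) reads "either Day 10, 14 or at premature study drug discontinuation".

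**ECGs, everyone.** The schedule tables (Protocol section 4; SAP Table 1) mark the ECG at Screening and Day 14 only. The Early termination cell is empty. Footnote 4 adds repeats for hydroxychloroquine patients alone: "the 12-lead ECG will be repeated after 3 hours" from the initial dose, and on Days 2 and 4. SAP 8.7 follows the same pattern.

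**After an early stop.** Under Protocol 10.3, patients who stop treatment and "remain in the study, will continued to be monitored per the Schedule of Assessments until Day 14".

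**Analysis.** SAP 8.7 summarises the incidence of abnormal and clinically significant abnormal ECGs. Table 14.3.5.1 does this by visit, time point and treatment group. The only subset named is hydroxychloroquine users (Table 14.3.5.2). ECG evaluation is a listed safety endpoint (Protocol 13.4).

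**The concern.** (a) The days named in 12.1.4 do not fit the dosing rule. Day 28 lies in off-drug follow-up, and Day 10, a planned last dosing day, is absent. The clause on premature discontinuation does not clearly fill the gap, because SAP 6.2 counts Day 10 finishers as having completed treatment per protocol. A site that read only the named days could miss the last on-drug ECG in the patients whose QT was meant to be watched most closely.

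(b) A reader would naturally take the Day 14 row of Table 14.3.5.1 as on-treatment ECG safety. For some patients it is not. If a drug effect on the ECG fades after dosing stops, off-drug recordings would dilute the abnormality rate in the opaganib arm, and the table gives no way to see this.

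**Working it through.** **Check of the dosing length.** Protocol 10.1 gives maximum participation as 45 days: up to 3 days of screening, 2 weeks of treatment and 4 weeks of follow-up.
- 3 + 14 + 28 = 45, which reproduces the stated figure.
- With 28 days of dosing: 3 + 28 + 28 = 59, which does not match.

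Dosing therefore cannot run past Day 14. For a full-course patient, Day 28 is 28 − 14 = 14 days after the last dose. Protocol 7.4 also still mentions 4 weeks of dosing, where the synopsis says up to 14 days and SAP 2.4 says 2 weeks. This suggests text left over from a longer regimen, although the documents do not say so.

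**(a) Hydroxychloroquine patient finishing on Day 10.**
- If only the days named in 12.1.4 are followed, the on-drug ECGs are at 3 hours, Day 2 and Day 4, which is 3.
- Gap from the last of these to the last dose: 10 − 4 = 6 days.
- With Day 10 restored: 3 + 1 = 4 on-drug ECGs.

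This loss arises only if a site follows the named days and disregards the words tying the ECG to the end of treatment.

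**(b) Patient not on hydroxychloroquine.** Time off drug at the Day 14 ECG = 14 − (day of last dose).

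| Patient | Last dose | Days off drug at Day 14 |
|---|---|---|
| Full course | Day 14 | 14 − 14 = 0 |
| Planned Day 10 finisher | Day 10 | 14 − 10 = 4 (4 × 2 = 8 twelve-hourly doses) |
| Early stopper who stays in the study | Day d, 1 to 13 | 14 − d |

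The Day 10 finisher has no scheduled ECG after screening while on drug. An early stopper is more than 4 days off drug at Day 14 if dosing ended before Day 10, and 1 to 3 days off if it ended on Days 11 to 13. The extreme, 14 − 1 = 13 days, needs a patient who stopped on Day 1, stayed in the study and had the Day 14 ECG. It is a bound, not a typical value.

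A Day 10 finisher on hydroxychloroquine is also due the Day 14 ECG, and that off-drug recording enters the same row.

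**What cannot be computed.** The documents give no expected share of Day 10 finishers or early stoppers, and no half-life for opaganib. Neither the share of off-drug recordings nor the size of any dilution can be derived.

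**The case against.** The best case for the plan is this. In 12.1.4 the operative instruction is an ECG at end of treatment. The bracket only illustrates it, and the synopsis has the correct days. For other patients, nothing in the documents requires an on-drug ECG. The sponsor placed the extra ECGs where QT risk was expected and excluded patients with "Corrected QT (QTc) interval on electrocardiogram (ECG) >470 ms for females or >450 ms for males". It also had reassuring data from the earlier solid-tumour study, which treated 21 patients at up to 750 mg twice daily: "No patient developed clinically significant ECG abnormalities on study. There were no treatment group differences noted for the changes from baseline of QTcF". In a proof-of-concept trial of about 40 patients with no formal inference, a sparse ECG schedule is a defensible choice.

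There are also safeguards. The hydroxychloroquine bullet encourages collecting QT data from patients on monitors, though its reach to other patients is arguable and it is not a scheduled 12-lead ECG. Protocol 15.5 has clinically significant ECG changes recorded as adverse events, whether or not the ECG was required. SAP 5.1 includes unscheduled values in summaries of clinically significant abnormalities. ECG and exposure listings are planned, so the recordings could be separated by hand.

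Most of this stands. It removes any case for more ECGs and keeps the point small. It does not make Day 28 an end-of-treatment day, and it does not separate the recordings in the summary table.

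A reader might also infer a problem from SAP 5.5, which assigns Early termination assessments to the nearest scheduled day. That rule applies only where the scheduled day's data are missing, and no ECG is scheduled at Early termination, so it has little to act on. A recording moved this way would typically be closer to the last dose than a Day 14 one.

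**Conclusion.** Both parts hold, and both are minor.

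(a) The named days in 12.1.4 are wrong. They conflict with the dosing rule in 10.1 and with the synopsis. At most, a Day 10 finisher on hydroxychloroquine would have 3 on-drug ECGs instead of 4, and only under a literal reading of the bracket.

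(b) The Day 14 row pools recordings made on the last dosing day with recordings made 4 days off drug in planned Day 10 finishers, and at other intervals in early stoppers who stay in the study. This follows from the schedules, Protocol 10.1 and 10.3, and SAP 8.7. It assumes that the Day 14 ECG is taken as scheduled.

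Stronger readings are tempting but unsupported. A reader might infer that QT monitoring of hydroxychloroquine patients is lost; they keep the three early on-drug ECGs, and the end-of-treatment wording still governs. A reader might infer that off-drug recordings dominate the row, or that 13 days off drug is common; the documents give no numbers for either. A reader might infer a bias between arms; nothing in the documents shows that the mix differs by arm. No efficacy endpoint is affected.

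**What to change.** 1. In Protocol 12.1.4, replace Day 14 and Day 28 with Day 10 and Day 14, as in the synopsis. This is a wording change. Table 1 has no Day 10 visit, so for a patient already discharged a Day 10 ECG would mean an extra attendance. The synopsis already asks for it, and the text applies only where possible and where hospital rules allow.

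2. In SAP 8.7 and Table 14.3.5.1, tabulate ECGs taken on or before the date of last dose separately from those taken after it. SAP 8.2.1 already uses the last day of treatment, so no new data are needed, and the change can be made even if patient visits are nearly finished, as SAP 3.5.2 suggests.

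The costs of item 2 are some sparse cells in a trial of about 40 patients, and a cut-off that is a convention: an ECG the day after the last dose counts as off drug, and no half-life in the documents supports a different cut. The split depends on what happened after randomisation, so it should be read descriptively. It recovers no on-drug data for Day 10 finishers; it only labels what was recorded. No added ECGs are requested.

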#### 12.1.5 Safety Follow-up (28 days after last dose of study drug)

- Concomitant medications
- Adverse Events
- Physical exam
- Vital signs (temperature, blood pressure, pulse rate, respiratory rate and oxygen saturation by pulse oximeter)
- Oxygen requirement (L/min)

#### 13 STUDY ENDPOINTS

## 13.1 Primary

The total oxygen requirement (area under the curve) using the daily oxygen flow (L/min) over 14 days (Day 1 to Day 14)

#### 13.2 Secondary

- 1) Time to 50% reduction from baseline in supplemental oxygen based on oxygen flow in L/min
- 2) The percentage of patients no longer receiving supplemental oxygen for at least 24 hours by Day 14
- 3) The time to two consecutive negative swabs for SARS-CoV-2 by PCR, at least 24 hours apart
- 4) The percentage of patients with at least two consecutive negative swabs, followed by continued negative swabs, for SARS-CoV-2 by PCR at Day 14
- 5) The percentage of patients requiring intubation and mechanical ventilation by the end of the 2-week off-study-drug follow-up
- 6) The time to intubation and mechanical ventilation
- 7) The percentage of patients with at least one measurement of fever at baseline (defined as temperature >38.0 C[100.4 F]), who are afebrile (defined as temperature <37.2C [99 F]) at Day 14
- 8) Mortality due to any cause at Day 30

## 13.3 Exploratory

The change in systemic markers of inflammation (D-dimer, cardiac troponin, C-reactive protein [CRP], lactate dehydrogenase [LDH] and ferritin) from baseline at Day 14

## 13.4 Safety

- 1) Incidence rates of all treatment-emergent AEs (TEAEs) and SAEs
- 2) Evaluation of vital signs
- 3) Evaluation of laboratory parameters (chemistry and hematology)
- 4) Evaluation of electrocardiograms (ECG)

#### 14 SAFETY REPORTING

All adverse events should be reported from first dose to the sponsor on the provided data-capture forms. All serious adverse events should be reported within 24 hours of knowledge. If the serious adverse event results in a fatal or life threatening outcome, the sponsor and the medical monitor must be notified immediately.

Complete and fax a Serious Adverse Event report form and provide any supporting documentation to the Medical Monitor at the Fax number or email provided above.

To discuss SAE with Medical Monitor, contact him directly by phone at the numbers provided above.

Follow-up information to a serious AEs must be provided to the Medical Monitor within 24 hours of investigator awareness in the same manner detailed above.

These serious adverse event reporting timelines must be followed in order for the sponsor to submit the safety information to the FDA within the safety reporting time regulations.

The medical monitor will notify all sites of any suspected, unexpected, serious adverse reactions (SUSARs). It is each Investigator's responsibility to forward all SUSAR reports that are provided by the sponsor to their local IRB/EC. The sponsor will forward all SUSAR reports to central IRBs.

#### 15 ADVERSE EVENTS DEFINITIONS

The following definitions of terms are guided by the United States Code of Federal Regulations (21 CFR 312.32(a)) and are included here.

An *Adverse Event (AE)* is defined as any untoward medical occurrence associated with the use of a drug in humans, whether or not considered drug related. An AE (may also be referred to as an adverse experience) can therefore be any unfavorable and unintended sign (including an abnormal laboratory finding, for example), symptom, or disease temporally associated with the use of a medicinal (investigational or marketed) product, whether or not considered related to the medicinal (investigational or marketed) product and from any route of administration, formulation, or dose, including an overdose.

A *Serious Adverse Event (SAE)* is any untoward medical occurrence that at any dose results in any of the following outcomes:

- death:
- is a life-threatening adverse event (defined as an event in which the subject was at risk of death at the time of the event; it does not refer to an event that hypothetically might have caused death if it were more severe);
- requires in-patient hospitalization or causes prolongation of existing hospitalization;
- a persistent or significant disability/incapacity or substantial disruption of the ability to conduct normal life functions;
- a congenital anomaly/birth defect;
- is an important medical event. This is defined as a medical event that may not be immediately life-threatening or result in death or hospitalization but, based upon appropriate medical and scientific judgment, may jeopardize the subject and may require medical or surgical intervention to prevent one of the other serious outcomes listed in the definition above. Examples of such events include, but are not limited to, intensive treatment in an emergency room or at home for allergic bronchospasm; blood dyscrasias or convulsions that do not result in hospitalization.

If either the sponsor or investigator believes that the event is serious, the event must be considered serious and be evaluated by the Sponsor for expedited reporting.

A *suspected adverse reaction* means any adverse event for which there is a reasonable possibility that the drug caused the adverse event.

An adverse event or suspected adverse reaction is considered *unexpected* if it is not listed in the Investigator's Brochure or is not listed at the specificity or severity that has been observed.

A Suspected Unexpected Serious Adverse Reaction (SUSAR) is any (suspected) adverse reaction (any adverse event for which there is a reasonable possibility that the drug caused the adverse event) that is both serious and unexpected.

